7.6. Concomitant medications/products and concomitant vaccinations

At each study visit, the investigator should question the subject's parent(s)/LAR(s) about any medications/products taken and vaccinations received by the subject.

7.6.1. Recording of concomitant medications/products and concomitant vaccinations

The following concomitant medication(s)/product(s)/vaccine(s) must be recorded in the eCRF.

- All concomitant medications/products, except vitamins and dietary supplements, administered in the 30 day follow-up period after the administration of each dose of study vaccines (Day 0 to Day 29).
- Any concomitant vaccination administered in the period starting 30 days before the first dose of study vaccines and ending at the last study visit (Day -29 to Day 730).
- Prophylactic medication (i.e. medication administered in the absence of ANY symptom and in anticipation of a reaction to the vaccination or blood sampling).
 - E.g. an anti-pyretic is considered to be prophylactic when it is given in the absence of fever and any other symptom, to prevent fever from occurring [fever is defined as temperature $\geq 37.5^{\circ}\text{C}/99.5^{\circ}\text{F}$ for oral, axillary or tympanic route, or $\geq 38.0^{\circ}\text{C}/100.4^{\circ}\text{F}$ for rectal route].
 - E.g. a topical local anesthetic used prior to a blood sampling is considered to be prophylactic.
- Any concomitant medications/products/vaccines listed in Section [7.6.2](#).
- Any concomitant medications/products/vaccines relevant to a SAE to be reported as per protocol or administered at any time during the study period for the treatment of a SAE. In addition, concomitant medications relevant to SAEs need to be recorded on the expedited Adverse Event report.
- Any antipyretic administered in the period starting 6 hours before vaccination and ending 12 hours after vaccination need to be recorded on the specific page of the eCRF.

7.6.2. Concomitant medications/products/vaccines that may lead to the elimination of a subject from ATP analyses

The use of the following concomitant medications/products/vaccines will not require withdrawal of the subject from the study but may determine a subject's evaluability in the ATP analysis. See Section [11.5](#) for cohorts to be analyzed.

- Any investigational or non-registered product (drug or vaccine) other than the study vaccine used during the study period.
- Immunosuppressants or other immune-modifying drugs administered chronically (i.e. more than 14 days in total) during the study period. For corticosteroids, this will mean prednisone ≥ 0.5 mg/kg/day (for pediatric subjects), or equivalent. Inhaled and topical steroids are allowed.
- Long-acting immune-modifying drugs administered at any time during the study period (e.g. infliximab).

- A vaccine not foreseen by the study protocol administered during the period starting 30 days before the first dose and ending 30 days after the last dose of vaccines administration*, with the exception of:
 - Scheduled routine pediatric vaccines which may be administered ≥ 14 days before a dose and ≥ 7 days after a dose of study vaccines.
 - Vaccines needed for urgent individual medical need (e.g. rabies prophylaxis).
- * In case an emergency mass vaccination for an unforeseen public health threat (e.g.: a pandemic) is organized by the public health authorities, outside the routine immunization program, the time period described above can be reduced if necessary for that vaccine provided it is licensed and used according to its Summary of Product Characteristics or Prescribing Information and according to the local governmental recommendations and provided a written approval of the sponsor is obtained.
- Immunoglobulins and/or any blood products administered during the study period.

8. HEALTH ECONOMICS

Not applicable.

9. SAFETY

The investigator or site staff is/are responsible for the detection, documentation and reporting of events meeting the criteria and definition of an AE or SAE as provided in this protocol.

Each subject's parent(s)/LAR(s) will be instructed to contact the investigator immediately should they/the subject manifest any signs or symptoms they perceive as serious.

9.1. Safety definitions

9.1.1. Definition of an adverse event

An AE is any untoward medical occurrence in a clinical investigation subject, temporally associated with the use of a medicinal product, whether or not considered related to the medicinal product.

An AE can therefore be any unfavorable and unintended sign (including an abnormal laboratory finding), symptom, or disease (new or exacerbated) temporally associated with the use of a medicinal product. For marketed medicinal products, this also includes failure to produce expected benefits (i.e. lack of efficacy), abuse or misuse.

Examples of an AE include:

- Significant or unexpected worsening or exacerbation of the condition/indication under study.

- Exacerbation of a chronic or intermittent pre-existing condition including either an increase in frequency and/or intensity of the condition.
- New conditions detected or diagnosed after investigational vaccine(s) administration even though they may have been present prior to the start of the study.
- Signs, symptoms, or the clinical sequelae of a suspected interaction.
- Signs, symptoms, or the clinical sequelae of a suspected overdose of either investigational vaccine(s) or a concurrent medication (overdose per se should not be reported as an AE/SAE).
- Signs, symptoms temporally associated with vaccine(s) administration.
- Significant failure of expected pharmacological or biological action.

AEs to be recorded as endpoints (solicited AEs) are described in Section 9.1.3. All other AEs will be recorded as UNSOLICITED AEs.

Examples of an AE DO NOT include:

- Medical or surgical procedures (e.g. endoscopy, appendectomy); the condition that leads to the procedure is an AE/SAE.
- Situations where an untoward medical occurrence did not occur (e.g. social and/or convenience admission to a hospital, admission for routine examination).
- Anticipated day-to-day fluctuations of pre-existing disease(s) or condition(s) present or detected at the start of the study that do not worsen.
- Pre-existing conditions or signs and/or symptoms present in a subject prior to the first study vaccination. These events will be recorded in the medical history section of the eCRF.

9.1.2. Definition of a serious adverse event

A SAE is any untoward medical occurrence that:

- a. Results in death,
- b. Is life-threatening,

Note: The term ‘life-threatening’ in the definition of ‘serious’ refers to an event in which the subject was at risk of death at the time of the event. It does not refer to an event, which hypothetically might have caused death, had it been more severe.

- c. Requires hospitalization or prolongation of existing hospitalization,

Note: In general, hospitalization signifies that the subject has been admitted at the hospital or emergency ward for observation and/or treatment that would not have been appropriate in the physician’s office or in an out-patient setting. Complications that occur during hospitalization are also considered AEs. If a complication prolongs hospitalization or fulfills any other serious criteria, the event will also be considered

serious. When in doubt as to whether ‘hospitalization’ occurred or was necessary, the AE should be considered serious.

Hospitalization for elective treatment of a pre-existing condition (known or diagnosed prior to informed consent signature) that did not worsen from baseline is NOT considered an AE.

d. Results in disability/incapacity

Note: The term disability means a substantial disruption of a person’s ability to conduct normal life functions. This definition is not intended to include experiences of relatively minor medical significance such as uncomplicated headache, nausea, vomiting, diarrhea, influenza like illness, and accidental trauma (e.g. sprained ankle) which may interfere or prevent everyday life functions but do not constitute a substantial disruption.

Medical or scientific judgment should be exercised in deciding whether reporting is appropriate in other situations, such as important medical events that may not be immediately life-threatening or result in death or hospitalization but may jeopardize the subject or may require medical or surgical intervention to prevent one of the other outcomes listed in the above definition. These should also be considered serious. Examples of such events are invasive or malignant cancers, intensive treatment in an emergency room or at home for allergic bronchospasm, blood dyscrasias or convulsions that do not result in hospitalization.

9.1.3. Solicited adverse events

9.1.3.1. Solicited local (injection-site) adverse events

The following local (injection-site) AEs will be solicited:

Table 16 Solicited local adverse events

All age groups
Pain at injection site
Redness at injection site
Swelling at injection site

9.1.3.2. Solicited general adverse events

The following general AEs will be solicited:

Table 17 Solicited general adverse events

Infant
Drowsiness
Fever*
Irritability/Fussiness
Loss of appetite

* Fever is defined as temperature $\geq 37.5^{\circ}\text{C}/99.5^{\circ}\text{F}$ for oral, axillary or tympanic route, or $\geq 38.0^{\circ}\text{C}/100.4^{\circ}\text{F}$ for rectal route. The preferred route for recording temperature in this study will be axillary.

Note: Temperature will be recorded in the evening. Should additional temperature measurements be performed at other times of day, the highest temperature will be recorded in the eCRF.

9.1.4. Clinical laboratory parameters and other abnormal assessments qualifying as adverse events or serious adverse events

In absence of diagnosis, abnormal laboratory findings (e.g. clinical chemistry, hematology, urinalysis) or other abnormal assessments (e.g. physical examination) that are judged by the investigator to be clinically significant will be recorded as AE or SAE if they meet the definition of an AE or SAE (refer to Sections 9.1.1 and 9.1.2). Clinically significant abnormal laboratory findings or other abnormal assessments that are present at baseline and significantly worsen following the start of the study will also be reported as AEs or SAEs.

The investigator will exercise his or her medical and scientific judgment in deciding whether an abnormal laboratory finding or other abnormal assessment is clinically significant.

9.1.5. Adverse events of specific interest

9.1.5.1. Spontaneous or excessive bleeding

Any episode of spontaneous or excessive bleeding occurring within 30 days after each vaccination should be fully investigated with a full range of hematological tests to identify the underlying cause and reported as an AE of specific interest.

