6.6.11.2. Blood sampling for hematology and biochemistry

- A volume of maximum 1.2 mL of whole blood should be drawn from all infants for analysis of the hematology parameters (refer to [Table 11](#)) at each pre-defined timepoint.
- A volume of maximum 1.1 mL of whole blood should be drawn from all infants for analysis of the biochemistry parameters (refer to [Table 11](#)) at each pre-defined timepoint.

Hematology and biochemistry parameters assessment will be performed according to laboratory practices.

[figure not shown]
Day 7 hematology testing will be performed if any \geq Grade 1 for platelet decrease is detected on Day 1. Similarly, hematology testing on Day 37 will be performed if any \geq Grade 1 for platelet decrease is detected on Day 31 (refer to [Figure 2](#) and [Appendix C](#)).

If any Grade 1 abnormality with potential clinical relevance (according to investigators judgment, refer to the [glossary of terms](#)) or any \geq Grade 2 abnormality is detected (refer to [Figure 2](#) and [Appendix C](#)):

- at **Screening**, for infants with hematological/biochemical values out of normal range which are expected to be temporary, a re-screening visit may be scheduled during which blood sample collection for hematology/biochemistry will be repeated (maximum one re-screening visit per infant is allowed within the interval planned in [Table 6](#)).
- at **Day 7**, the relevant hematology/biochemistry parameter(s) **must** be re-tested before administration of vaccine Dose 2, either during an unscheduled visit or at the Dose 2 vaccination visit itself (provided results are obtained before vaccination). Only if the concerned parameter(s) is/are within the acceptable range (i.e. within normal range or Grade 1 without clinical relevance), vaccine Dose 2 can be administered. If the concerned parameter(s) is/are not within the acceptable range within the allowed interval for the second dosing visit, Visit 5, the infant will not receive Dose 2 but should still continue the study for safety follow-up (up to Day 730).
- at **Days 30, 37 and 60** the relevant hematology/biochemistry parameter(s) **may** be re-tested as per the opinion of the investigator.

Note: For safety reasons and specifically for further investigation of an AE of specific interest (suspected bleeding or low platelet count), blood can be re-sampled for hematology and biochemistry assessment.

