The time period for collecting AEs of specific interest (RSV-LRTI) will begin at the first receipt of study vaccine and will end at study conclusion. The time period for collecting AEs of specific interest (spontaneous or excessive bleeding) will begin at the first receipt of study vaccine and will end 30 days after the last vaccination. See Section 9.4 for instructions on reporting of AEs of specific interest.

An overview of the protocol-required reporting periods for AEs, AEs of specific interest and SAEs is given in [Table 18](#).

Table 18 Reporting periods for collecting safety information

Visit Days	SCR -29 to 0	V1 0	V2 1	V3 3	6	V4 7	29	V5 30	V6 31	V7 33	36	V8 37	59	V9 60	V10 365	V11 730	
Solicited local and general AEs		■						■									
Unsolicited AEs		■															
Clinical examination with special attention given to the detection of episodes of spontaneous bleeding or easy bruising and evidence of bruising or petechiae*			■							■							
Examination of limb for petechiae induced by the tourniquet**			■							■							
AEs/SAEs leading to withdrawal from the study		■															
AE of specific interest (RSV-LRTI)		■															
AE of specific interest (spontaneous or excessive bleeding)		■															
SAEs		■															

CONFIDENTIAL

204838 (RSV PED-002)
Protocol Amendment 4 Final

Visit	SCR	V1	V2	V3		V4		V5	V6	V7	V8		V9	V10	V11		
Days	-29 to 0	0	1	3		6	7	29	30	31	33	36	37	59	60	365	730
SAEs related to study participation (start at signature of informed consent form) or concurrent GSK medication/vaccine																	

SCR: Screening

* Clinical examination with special attention given to the detection of spontaneous bleeding or easy bruising and evidence of bruising or petechiae will be performed by the investigator/study staff on Day 1, Day 3, and Day 7 after each vaccination. The visits on Day 3 and Day 33 may be replaced by a phone call by the investigator/study staff to inquire of the infants' general health and to solicit reports of a rash, spontaneous bleeding or easy bruising. Subjects' parent(s)/LAR(s) will be instructed to contact the investigator/study staff if their child presents symptoms of spontaneous bleeding or easy bruising or if their child develops a rash in the month following vaccination, in order to detect any thrombocytopenic petechiae or purpura.

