Once an Investigator becomes aware that an AE of specific interest (RSV-LRTI and spontaneous or excessive bleeding) has occurred in a subject, the Investigator (or designate) must complete the information in the electronic Expedited Adverse Events Report WITHIN 24 HOURS. The report will always be completed as thoroughly as possible with all available details of the event. Even if the Investigator does not have all information regarding an AE of specific interest (RSV-LRTI and spontaneous or excessive bleeding), the report should still be completed within 24 hours. Once additional relevant information is received, the report should be updated WITHIN 24 HOURS.

The Investigator will always provide an assessment of causality at the time of the initial report. The Investigator will be required to confirm the review of causality by ticking the 'reviewed' box in the electronic Expedited Adverse Events Report within 72 hours of submission of the AE of specific interest.

Refer to Section 9.4.4.1 for the back-up system in case the electronic reporting system does not work.

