9.10.2. Internal safety review committee (iSRC) oversight

This study will be overseen by an iSRC operating under a charter. Core members of the iSRC will include a GSK Biologicals' safety physician, a CRDL, and a biostatistician who are not otherwise involved in the conduct of the project. The iSRC safety reviews will be conducted using unblinded data. The iSRC has access to the subject randomization and reviews unblinded data.

The iSRC will review all accumulating safety data three weeks after the start of vaccination and then about every three weeks (until the IDMC has reviewed all safety data up to 30 days after administration of Dose 2 in Step 3 (i.e. Day 60)). The iSRC members will determine if a safety signal should be escalated to the IDMC. The iSRC members will determine whether any of the predefined holding rules are met (refer to Section 9.10.5) or if there is any other safety signal. In this case, vaccination in the study will be immediately put on hold (refer to Section 9.10.6).

The iSRC will receive the following safety data within 48 hours upon GSK becoming aware of:

- Fatal SAEs.
- Life-threatening SAEs.

- Related SAEs.
- SAEs occurring within 30 days of vaccination.
- LRTI associated with RSV infection (AE of specific interest) occurring from Day 0 to Day 730.
- Spontaneous or excessive bleeding (AE of specific interest) occurring within 30 days after each vaccination.

In addition, the iSRC will receive:

- Unblinded summary reports of accumulated solicited AEs, unsolicited AEs, results of laboratory monitoring of hematology and biochemistry.
- New information that may adversely affect the safety of the subjects or the conduct of the study.
- All subsequent protocol amendments, informed consent changes or revisions or other documents originally submitted for review.
- All subsequent protocol administrative changes (for information).

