9.10.3. Independent Data Monitoring Committee (IDMC) oversight

This study will be overseen by an IDMC operating under a charter. Overall, the role of the IDMC includes the review and protection of data integrity and rights and safety of study participants throughout the study period. It will provide initial, regular, and closing advice to GSK Biologicals on medical, ethical, scientific and safety-related issues. Its advice will be based on the interpretation of study data with reference to the study protocol.

The IDMC will review the protocol and statistical analysis plan. Meetings will be documented and minutes of open sessions of the IDMC meetings made available to the sponsor. The IDMC may, if deemed necessary, convene a meeting with, or request further information from the principal investigators and GSK Biologicals' designated project representatives at any stage of the study.

The IDMC may recommend to the sponsor to suspend the enrolment to the study and/or vaccination based on their review of safety data arising in this study (refer to Section [9.10.6](#)).

The IDMC safety reviews will be conducted using unblinded data. The IDMC will review all available safety data while taking into account any other findings that could have an impact on the safety of the subjects.

The IDMC members will determine whether any of the predefined study holding rules are met (refer to Section [9.10.5](#)) or if there is any other safety signal. If this is the case, vaccination in the study will be immediately put on hold. If no safety signal is observed, the favorable outcome of the safety evaluation authorizing the investigator to proceed with vaccination of infants as outlined in [Figure 1](#), will be also documented and provided in writing.

- The IDMC will receive the following safety data within 48 hours upon GSK becoming aware of:
 - Fatal SAEs occurring from Day 0 to Day 730.
 - Life-threatening SAEs occurring from Day 0 to Day 730.
 - Related SAEs occurring from Day 0 to Day 730.
 - SAEs occurring within 30 days of vaccination.
 - LRTI associated with RSV infection (AE of specific interest) occurring from Day 0 to Day 730.
 - Spontaneous or excessive bleeding (AE of specific interest) occurring within 30 days after each vaccination.
- The IDMC will receive the following safety data monthly throughout the period of vaccination (up to 30 days after administration of Dose 2 in Step 3, i.e. Day 60):

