 - Summary reports of solicited and unsolicited AEs, SAEs and laboratory toxicity.
- The IDMC will receive the following safety data approximately monthly from beginning of the first RSV season and the frequency will be adapted based on the instruction of the IDMC:
 - Cumulative reports of the incidence of RSV-RTI, RSV-LRTI, RSV-severe LRTI and RSV-RTI leading to hospitalization.
 - Cumulative tables of incidence of all SAEs.

In addition, the IDMC will receive from GSK Biologicals:

- New information that may adversely affect the safety of the subjects or the conduct of the study.
- All subsequent protocol amendments, informed consent changes or revisions or other documents originally submitted for review.
- All subsequent protocol administrative changes (for information).

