9.10.5. Holding rules

The safety holding rules which will be assessed by the investigator are defined in [Table 21](#) and the safety holding rules which will be assessed by the iSRC and the IDMC during the safety evaluation are defined in [Table 22](#).

Table 21 Holding rules assessed by the investigator

Holding Rule	Event	Number of infants/group		
		Step 1	Step 2	Step 3
1a	Death or any life-threatening serious adverse event (SAE) that can be causally related to vaccination, according to investigator's assessment.	≥ 1	≥ 1	≥ 1
1b	Any withdrawal from the study (by investigator or parent(s)/LAR(s) of the subject request) following a Grade 3 AE that cannot reasonably be attributed to a cause other than vaccination.	≥ 1	≥ 1	≥ 1
1c	Any local or general solicited AE leading to hospitalization that cannot reasonably be attributed to a cause other than vaccination.	≥ 1	≥ 1	≥ 1
1d	Within 30 days post-vaccination, Any spontaneous local or general bleeding AND Thrombocytopenia < 50000/mm ³	≥ 1	≥ 1	≥ 1

If an investigator detects one of the holding rules mentioned above, he/she will immediately put the enrolment or the vaccination on hold (refer to Section 9.10.6) and he/she will immediately inform the sponsor and enter the data in the eCRF. It is sponsor's responsibility to put the enrolment or the vaccination on hold at all sites.

Table 22 Holding rules during the planned iSRC and IDMC evaluation

Holding Rule	Event	Number of infants/group		
		Step 1	Step 2	Step 3
2a	Any Grade 3 solicited local AE lasting 48 hours or more in an investigational RSV vaccine group, within the 7-day (Days 0-6) post-vaccination period.	≥ 25% & ≥ 2 infants/group	≥ 25% & ≥ 2 infants/group	≥ 25% & ≥ 2 infants/group
2b	Any Grade 3 solicited general AE lasting 48 hours or more in an investigational RSV vaccine group, that cannot reasonably be attributed to a cause other than vaccination, within the 7-day (Days 0-6) post-vaccination period.	≥ 25% & ≥ 2 infants/group	≥ 25% & ≥ 2 infants/group	≥ 25% & ≥ 2 infants/group

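### A platelet count below 50,000/mm³ without bleeding does not by itself trigger rapid reporting to the sponsor, the iSRC or the IDMC, although Protocol 6.6.11.2 treats low platelets as an AE of specific interest

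*Protocol*

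**What the plan says.** Protocol 1.2.4.1 and 11.4 name thrombocytopenia as the a priori concern. Under 11.4, one Grade 3 or higher case in a vaccinee may lead the IDMC to recommend continuing at the lower dose.

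The reporting sections are narrower. Protocol 9.1.5 defines two AESIs: bleeding ("Any episode of spontaneous or excessive bleeding occurring within 30 days after each vaccination should be fully investigated") and RSV-LRTI. Later sections repeat that pair:

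- 9.3.1, collection period: "AEs of specific interest (spontaneous or excessive bleeding) will begin at the first receipt of study vaccine and will end 30 days" after the last dose.
- 9.4.1 and Table 20: 24 hours to the sponsor for SAEs and the two AESIs.
- 9.4.3, expedited report: required once the investigator learns that "an AE of specific interest (RSV-LRTI and spontaneous or excessive bleeding) has occurred in a subject".
- 9.10.2 and 9.10.3, 48-hour lists: certain SAEs, RSV-LRTI and "Spontaneous or excessive bleeding (AE of specific interest) occurring within 30 days" after each vaccination.

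Laboratory data otherwise travel on the periodic cycles. For the iSRC, "The iSRC will review all accumulating safety data three weeks after the start of vaccination and then about every three weeks". For the IDMC, the monthly package holds "Summary reports of solicited and unsolicited AEs, SAEs and laboratory toxicity".

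In 9.10.5, rule 1d is met by one infant but is conjunctive: "Any spontaneous local or general bleeding AND Thrombocytopenia" below 50,000/mm³. Rule 2c covers Grade 3 or higher laboratory values, but needs at least 25% and at least 2 infants in a vaccine group.

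Two places read more widely. Protocol 6.6.11.2 allows re-sampling "specifically for further investigation of an AE of specific interest (suspected bleeding or low platelet count"). SAP Annex 2, the preferred terms for AESI detection, has a thrombocytopenia block marked for immediate escalation, provided the term was already reported as an Expedited Adverse Event.

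**The concern.** The event that the protocol worries about most is covered by the rapid system only when the infant also bleeds. A silent count below 50,000/mm³ is Grade 3 or 4 in Appendix C and falls under the same threshold as rule 1d. Yet whether it reaches the committees quickly depends on how a blinded investigator classifies a local laboratory result. Under 9.1.4, even recording it as an AE is a matter of judgement.

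The affected infant has some protection. A platelet decrease of Grade 1 or higher on Day 1 triggers Day 7 testing, and a Grade 2 or higher Day 7 result blocks Dose 2 until a retest is acceptable (6.6.11.2, 7.5). The residual risk falls mainly on other infants. Vaccination can continue at up to 10 infants a day, and the 48-hour observation pause covers only the first eight in each step (9.10.1).

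**Working it through.** **The plan's own figures.** The text under Figure 4 (16 per group) reproduces with exact binomial tails.

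- Rule 1 (at least 1 of 16): not met at a true rate of 1%, 0.99^16 = 85.1%; met at 10%, 1 − 0.90^16 = 81.5%.
- Rule 2 (at least 4 of 16): not met at 10%, 93.2%; met at 25%, 59.5%, and at 26%, 63.0%.
- The 0.04% in 11.4: Φ((50 − 300)/75) = 0.0429% per count.

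**Can one silent case trigger anything automatically?**

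- 24-hour report (9.4.1, Table 20): no, unless judged an SAE.
- 48-hour lists (9.10.2, 9.10.3): no, unless judged an SAE.
- Rule 1d: no, because bleeding is required.
- Rule 2c: no. The 25% condition means 2 of 8 or 4 of 16 vaccinees.
- SAP Annex 2: no. It acts only on an Expedited report, which the protocol requires only for SAEs and the two AESIs.

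**Notification time.** As an AESI: 24 h (Table 20) + 48 h (9.10.2, 9.10.3) = 72 h. Without a judgement-based report, the wait is at most about 21 days for the iSRC and about a month for the IDMC's own summary. These are maxima; a case arising at random within a cycle waits about half as long on average.

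**How often it could arise.** Protocol 11.4 pairs a vaccinee mean of 190,000 with an SD of 47,500, giving Φ((50 − 190)/47.5) = 0.160% per count. The chance of at least one case with rule 2c unmet is P(at least 1) − P(2c met):

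| Vaccinees | One count each | Two independent counts (Days 1 and 31) |
|---|---|---|
| 8 | 1.275% − 0.007% = 1.27% | 2.53% − 0.03% = 2.50% |
| 16 | 2.53% | 5.00% |

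Checking 2c at 8 and again at 16 vaccinees gives 2.53% and 4.97%. All of these are upper bounds on the gap, because they are not reduced for cases reported as SAEs or accompanied by bleeding.

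**Reporting burden under no effect.** The chance of at least one extra report is 1 − (1 − 0.000429)^(N × counts). The range runs from one count per infant to four independent counts (Days 1, 30, 31, 60), the latter being an upper bound:

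- 32 infants: 1.36% to 5.35%
- 64 infants: 2.71% to 10.40%
- 96 infants: 4.04% to 15.19%

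Expected extra reports over 96 infants: 96 × 0.000429 = 0.04, up to 384 × 0.000429 = 0.16.

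**The case against.** The strongest reply is that a serious case would move quickly anyway. Protocol 9.1.2 says important medical events should be treated as serious and gives blood dyscrasias without hospitalization as an example. An SAE within 30 days of vaccination is on both 48-hour lists, so that route takes the same 72 hours. The investigator may also hold vaccination for a safety concern (9.10.6), and an ad hoc iSRC meeting can be called (1.2.4.2). This stands, and it rules out reading the documents as giving no prompt route at all. What remains is that the platelet value alone compels none of these steps. Both committees also receive new safety information, but with no deadline.

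Three other strong readings are tempting and are not supported:

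- *Only the committees can learn the allocation.* Section 9.8 gives the investigator direct emergency access, and under 9.7 the sponsor's safety physician unblinds unexpected related SAEs.
- *The IDMC is necessarily uninformed for a month.* The iSRC sees unblinded laboratory results about every three weeks, decides whether to alert the IDMC, and can stop vaccination for any safety signal (9.10.2).
- *Dose escalation could slip past the case.* The IDMC must review at least 16 two-dose subjects and give formal approval first (9.10.4), so the 11.4 decision does not depend on 72-hour notice.

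It is also fair to say that Annex 2 is a screening list. SAP template footnotes use its terms to find events potentially related to bleeding or LRTI, so it does not show that low platelets were meant as a separate AESI. The wording in 6.6.11.2 sits in a permission to re-sample and may simply be loose. Finally, both committees work under charters that are not among the documents and may contain laboratory alerts.

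**Conclusion.** The concern holds for the protocol and SAP text. A bleeding-free count below 50,000/mm³ has no automatic rapid route, one case meets no numeric holding rule, and 6.6.11.2 disagrees with 9.1.5 about whether low platelets are an AESI. If no judgement-based route is used, the plan as written leaves such a case to periodic review: at most about three weeks or a month, against about 72 hours.

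The size is modest. The 1.3% to 5.0% range assumes the 11.4 platelet scenario, normality and, at its upper end, independent counts; it bounds the gap from above. The conclusion rests on the reporting lists, not on these probabilities. It is a low-cost improvement to consider. It does not show that the safety monitoring fails.

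**What to change.** Add a third AESI to Protocol 9.1.5: *platelet count below 50,000/mm³ (Grade 3 or higher, Appendix C) at any post-vaccination sample up to and including Visit 9, with or without bleeding*. Naming Visit 9 matters because Table 6 allows it 28 to 35 days after Dose 2, which can fall outside the 30-day bleeding period.

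Carry the term into Table 5, 6.6.16, 9.3.1 with Table 18, 9.4.1, 9.4.3, 9.5.1, 9.10.2 and 9.10.3. This also settles the disagreement with 6.6.11.2.

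In the SAP, add it to Table 3 and tabulate it separately in 6.4.1.1. That section tabulates the bleeding AESI by the Section 12 terms, which include the thrombocytopenia block, so platelet events would otherwise be counted as bleeding.

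Leave the holding rules in 9.10.5 and 9.10.6 as they are. A pause after one case is a separate option for the sponsor and IDMC.

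The cost is modest rewording across both documents, with no extra blood draws, visits or infants, plus the small reporting burden shown in the working.
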